6.3 Withdrawal criteria

Subjects are free to withdraw from the study at any time, without prejudice to their continued care.

All subjects who withdraw from the study due to an AE must be followed until resolution of the event or until the event is considered stable.

Subjects **must** be withdrawn from the study if any of the following events occur:

1. Subject experiences intolerable AEs, including clinically relevant abnormal laboratory findings that, in the opinion of the investigator, preclude further participation in the study.
2. The sponsor or a regulatory agency requests withdrawal of the subject.
3. Female subject achieves menarche and does not practice contraception as provided in Exclusion Criterion 21, unless sexually abstinent.
4. Subject becomes pregnant, as evidenced by a positive pregnancy test.
5. Subject has QTc interval of ≥ 500 ms that is confirmed by a cardiologist overread on any ECG.
6. Subject develops second- or third-degree AV block.
7. Subject is unwilling or unable to continue, or the parent/legal representative is unwilling or unable to allow the subject to continue in the study.
8. Investigator decides that withdrawal from further participation would be in the subject's best interest.
9. Subject has a prolongation or worsening of overall seizure duration, frequency, type, or pattern considered by the investigator as serious enough to warrant discontinuation from the study.

10. Subject uses rescue medication in excess of that permitted by the protocol.
11. Subject needs any alteration in AED daily dose or VNS settings.
12. In the case of liver function test (LFT) results of transaminases (AST, ALT, or both) $\geq 3x$ ULN to $< 5x$ ULN and total bilirubin $\geq 2x$ ULN or transaminases (AST, ALT, or both) $\geq 5x$ ULN, LCM must be immediately discontinued and the subject withdrawn from the study. The LFTs will be repeated as soon as possible, and in no case > 1 week later.
13. For subjects ≥ 6 years of age, subject has actual suicidal ideation as indicated by a positive response ("Yes") to either Question 4 or Question 5 of the "Since Last Visit" version of the C-SSRS. The subject should be referred immediately to a Mental Healthcare Professional and must be withdrawn from the study.

Subjects **may** be withdrawn from the study if any of the following events occur:

1. Any clinically relevant change in medical or psychiatric condition (if in the opinion of the investigator, the change in condition warrants discontinuation from the study).
2. Subject requires a medication that is not permitted by the protocol (see Section 7.8).
3. Subject and/or delegated caregiver is unable to manage the completion of the diary or is noncompliant with study procedures or medication, in the opinion of the investigator.
4. Transaminases (AST, ALT, or both) $\geq 3x$ ULN to $< 5x$ ULN, in the presence of normal total bilirubin, will be repeated within a few days. If the repeat testing confirms the abnormality (ie, transaminases are $\geq 3x$ ULN to $< 5x$ ULN with normal bilirubin), then weekly monitoring of LFTs should continue until resolved (ie, $< 3x$ ULN or stable condition). The investigator is to decide whether or not to stop LCM.

Investigators should attempt to obtain information on subjects in the case of withdrawal or discontinuation. For subjects considered as lost to follow up, the investigator should make an effort (at least 1 phone call and 1 written message to the subject), and document his/her effort (date and summary of the phone call and copy of the written message in the source documents), to complete the final evaluation. All results of these evaluations and observations, together with a narrative description of the reason(s) for removing the subject, must be recorded in the source documents. The electronic Case Report form (eCRF) must document the primary reason for withdrawal or discontinuation.

Investigators should contact the medical monitor, whenever possible, to discuss the withdrawal of a subject in advance.

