Assessments	Baseline Period (6 weeks)		Treatment (18 weeks)												End of Study Period			Unscheduled Visit ^a		
	V1	TC 1	Titration Period (6 weeks)								Maintenance Period (12 weeks)				Taper Period (2-4 weeks) ^b		Safety Follow-Up (30 days)			
Visit			V2	TC 2	V3	TC 3	V4 ^c	V5 ^c	End of Titrat V6	TC 4	V7	TC 5	V8	TC 6	V9/ET ^d	TC 7 ^e	End of Taper Visit ^f	Safety FU Visit ^g	Safety FU TC ^g	At any time
Week in study	-6	-3	Day 1	1	2	3	4	5	6	8	10	12	14	16	18	19	20-22	22-24	24-26	
Health care resource use			X		X		X	X	X	X	X		X		X		X	X		

AE=adverse event; AED=antiepileptic drug; BP=blood pressure; BRIEF-P/BRIEF=Behavior Rating Inventory of Executive Function-Preschool Version/Behavior Rating Inventory of Executive Function; CBCL=Child Behavior Checklist; C-SSRS=Columbia Suicide Severity Rating Scale; ECG=electrocardiogram; EEG=electroencephalogram; ET=Early Termination; FU=Follow-Up; IXRS= interactive voice/web response system; LCM=lacosamide; PedsQL=Pediatric Quality of Life Inventory; TC=telephone contact; Titrat=Titration; V=Visit; VNS=vagus nerve stimulation

Note: For all visits outside of the Safety Follow-Up Period, a time window of ± 2 days relative to Visit 2 (Titration Period) is applicable. The schedule above displays the maximum possible study duration for a subject.

^a Unscheduled Visits may be performed at any time after Visit 1, at the discretion of the investigator. In addition to the required assessments indicated in the schedule above, the investigator can perform further assessments based on his/her clinical judgment and the medical needs of the subject (eg, assessments of ECG, laboratory tests, physical examination, neurological examination, etc).

^b The recommended Taper Period duration is up to a maximum of 4 weeks, but a slower or faster taper may be permitted if medically necessary. The End of Taper Visit will occur at the end of the last week of the Taper Period.

^c Visits 4 and 5 are optional and will only be required if a subject requires further LCM dose adjustment.

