6.2 Exclusion criteria

Subjects are not permitted to enroll in the study if any of the following criteria are met:

1. Subject has previously participated in this study, subject has been assigned to LCM in a previous LCM study, or subject has ever received LCM.
2. Subject is currently participating or has participated within the last 2 months in any study of an investigational drug or experimental device.
3. Subject has a history of convulsive status epilepticus within 1 month prior to Visit 1.
4. Subject has a current or previous diagnosis of pseudoseizures, conversion disorders, or other nonepileptic ictal events that could be confused with seizures.
5. Subject has exclusively typical absence (Type IIA1) or atypical absence (Type IIA2) seizures (no other generalized seizure types are reported), or has only partial-onset seizures (Type I).
6. Subject has primary generalized tonic-clonic seizures with a diagnosis of idiopathic generalized epilepsy.
7. Subject has any medical or psychiatric condition that, in the opinion of the investigator, could jeopardize the subject's health or would compromise the subject's ability to participate in this study.

8. Subject ≥ 6 years of age has a lifetime history of suicide attempt (including an actual attempt, interrupted attempt, or aborted attempt), or has suicidal ideation in the past 6 months as indicated by a positive response (“Yes”) to either Question 4 or Question 5 of the Columbia Suicide Severity Rating Scale (C-SSRS) at Screening.
9. Subject has a known hypersensitivity to any components of the investigational medicinal product (IMP).
10. Subject has a medical condition that could reasonably be expected to interfere with drug absorption, distribution, metabolism, or excretion.
11. Subject has a known history of severe anaphylactic reaction or serious blood dyscrasias.
12. Subject has any history of alcohol or drug abuse within the previous 2 years.
13. Subject has an acute or sub-acutely progressive central nervous system disease. Subject has epilepsy secondary to a progressing cerebral disease or any other progressively neurodegenerative disease (malignant brain tumor or Rasmussen Syndrome).
14. Subject has alanine aminotransferase (ALT), aspartate aminotransferase (AST), or total bilirubin levels $\geq 2x$ the upper limit of normal (ULN) or has alkaline phosphatase levels $\geq 3x$ ULN.
15. Subject has impaired renal function (ie, creatinine clearance is lower than 30mL/min) at Visit 1.

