8.2 Titration Period

8.2.1 Visit 2 (Day 1)

Subjects will be asked to return to the clinic on the morning of the day prior to Visit 2 (end of Week 0) to begin 24-hour ambulatory EEG recordings. Scalp electrodes will be attached, and subjects will receive a recording device. Subjects will be asked to return approximately

24 hours later (for Visit 2, Day 1) for removal of the scalp electrodes and return of the recording device. At Visit 2, the investigator should determine whether the subject is still eligible and willing to continue in the study.

The following will be performed prior to the first dose of LCM:

- Review inclusion/exclusion criteria.
- Concomitant AED(s) assessment.
- VNS assessment (for subjects with an implanted VNS device).
- Concomitant medication(s) assessment.
- Complete physical examination.
- Complete neurological examination.
- 12-lead ECG (2 interpretable recordings [20 to 30 minutes apart] to be performed prior to any blood draws and vital signs assessment and, if possible, with the subject in the supine position for approximately 5 minutes preceding the recordings and during the recordings. Recordings should be performed at least 15 minutes after removal of scalp electrodes used for the 24-hour ambulatory EEG recording).
- Vital signs (BP and pulse rate, including orthostatic assessments in ambulatory subjects).
- Body weight and height assessment.
- C-SSRS (if applicable).
- Blood sample for clinical chemistry and hematology.
- Blood sample for LCM and concomitant AED plasma concentrations (before dosing with LCM). Blood sample will be drawn along with clinical chemistry and hematology samples.
- Achenbach CBCL (if applicable); CBCL/1½-5 or CBCL/6-18 for pediatric subjects ≥18 months of age.
- Bayley Scales of Infant and Toddler Development®, Third Edition (Bayley-III Scales) (if applicable). For pediatric subjects <18 months of age at Baseline enrolled in English-speaking countries.
- BRIEF-P (≥2 years to <5 years of age)/BRIEF (≥5 years of age) (version consistent with age at the visit).
- PedsQL for subjects ≥1 month to ≤18 years of age (version consistent with age at the visit).
- Urine sample for urinalysis (if applicable).
- Urine pregnancy test (if applicable).
- Subject diary return/review.
- AE reporting.

- Review withdrawal criteria.
- Contact IXRS.
- Dispense subject diary.
- Reminder to complete subject diary on a daily basis.
- Health care resource use.

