8.3 Maintenance Period

8.3.1 Telephone contacts (Weeks 8, 12, and 16)

At the end of Weeks 8, 12, and 16 (± 2 days), the investigator or designee should contact the subject's caregiver (including parent/legal representative) by telephone. The assessments for these telephone contacts are the same as those performed during the telephone contact at Week -3 in Section 8.1.2 with the exception that inclusion/exclusion criteria do not need to be checked at Weeks 8, 12, and 16.

Subjects must titrate to at least 4mg/kg/day for subjects weighing <50kg, or 200mg/day (tablets/oral solution) for subjects weighing ≥ 50 kg in order to enter the Maintenance Period.

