11.7.11 Assessment of suicidality

Suicidality will be assessed by trained study personnel using the C-SSRS (Columbia University Medical Center, 2008). For subjects ≥ 6 years of age, this scale will be used for screening as well as to assess suicidal ideation and behavior that may occur during the study. The C-SSRS will be completed according to the tabular schedule of study procedures in Section 5.2.

The “Since Last Visit” version of the C-SSRS will be used, with the following exceptions:

- The “Baseline/Screening” version of the C-SSRS should be completed at Visit 1.
- If a subject turns 6 years of age during the study, the “Already Enrolled” version of the C-SSRS should be completed at the first visit after the sixth birthday.

The C-SSRS is not validated for subjects < 6 years of age and will not be used for this population. Subjects should be monitored for any changes in mood, ideas, or behavior for warning signs of depression. The investigator should be aware of common warning signs that might be a signal for risk of depression. For common signs and symptoms of depression in children younger than 6 years old, reference should be made to the current version of the Diagnostic and Statistical Manual of Mental Disorders. Parents and caregivers should also be advised accordingly and effort should be made at clinic visits to specifically assess potential depression.

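### After first dose the only mandatory suicidality stop covers C-SSRS ideation on one form; an on-study suicide attempt, or a 'Yes' on the 'Already Enrolled' form, is left to judgment

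*Protocol*

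**What the plan says.** Criterion 13 of the must-withdraw list in Protocol 6.3 applies to subjects aged 6 or over. It is met when the "subject has actual suicidal ideation as indicated by a positive response" to Question 4 or Question 5, and it names the 'Since Last Visit' version of the C-SSRS. Its second sentence sets the consequence: "The subject should be referred immediately to a Mental Healthcare Professional and must be withdrawn from the study".

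Three other places bear on it.

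- Exclusion 8 (Protocol 6.2) bars a subject aged 6 or over who "has a lifetime history of suicide attempt (including an actual attempt, interrupted attempt, or aborted attempt"), as well as one with recent Question 4 or 5 ideation at Screening. Eligibility is reviewed for the last time at Visit 2, before dosing, when "the investigator should determine whether the subject is still eligible and willing to continue in the study" (Protocol 8.2.1).
- Protocol 11.7.11 says the scale is used for screening and also "to assess suicidal ideation and behavior that may occur during the study".
- The same section makes an exception to the 'Since Last Visit' form for a child who turns 6 on study. The 'Already Enrolled' version "should be completed at the first visit after the sixth birthday". No action is attached to its answers.

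**The concern.** The protocol collects suicidal ideation and suicidal behavior, but ties a mandatory consequence to ideation alone. The lesser event stops treatment automatically and the greater one does not. The entry rule takes the opposite view of an attempt: one that disqualifies a child up to first dose meets no suicidality-specific rule the day after.

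Elsewhere Protocol 6.3 gives clear safety signals fixed triggers, such as a confirmed QTc of 500 ms or more, AV block and the liver thresholds. Suicidality has such a trigger too, but a narrow one. Mandatory withdrawal and mental-health referral sit together in criterion 13, so an attempt without a qualifying 'Yes' prompts neither by rule.

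The naming of a single form leaves a second, smaller hole. Read literally, a Question 4 or 5 'Yes' on the 'Already Enrolled' form falls outside criterion 13. At stake is whether a child on LCM is stopped and referred under a rule or by individual judgment.

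**Working it through.** **Which events have a suicidality-specific mandatory stop after first dose?** Taking every criterion in Protocol 6.3 together with 11.7.11:

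| Event after first dose, subject aged 6 or over | Suicidality-specific mandatory stop |
|---|---|
| Question 4 or 5 'Yes', 'Since Last Visit' form | Yes, criterion 13 |
| Actual, interrupted or aborted attempt | None |
| Question 4 or 5 'Yes', 'Already Enrolled' form | None |

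Exclusion 8 does not fill the second row. Table 5-1 schedules the eligibility check at Visit 1, the Week -3 call and Visit 2 only, and 8.2.2 and 8.3.1 drop it from later telephone contacts. SAP 11 only lists C-SSRS data and sets no stopping rule.

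**At which visits does the attempt gap apply?** The C-SSRS is required on treatment at Visits 3, 6, 7, 8 and 9, and at Visits 4 and 5 if held. Dosing continues after Visits 3 to 8 for everyone who stays on study. It also continues after Visit 9 for subjects who taper or enter SP848 (Protocol 8.3.4). Criterion 13 does not act on a behavior finding at any of them.

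**How many children does the 'Already Enrolled' gap concern?** Protocol 5.1.2 plans approximately 40 subjects aged 4 to <18 and sets no quota within that range. Assume an even spread over 14 years of age:

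- Density: 40 / 14 = 2.857 subjects per year of age.
- Turning 6 between Visit 2 and Visit 9 (18 weeks): 2.857 × 18 / 52.18 = 0.99.
- Turning 6 between Visit 2 and Visit 8 (14 weeks): 2.857 × 14 / 52.18 = 0.77.
- Sensitivity, all 40 aged 4 to <12: 40 / 8 = 5.0 per year of age, giving 5.0 × 18 / 52.18 = 1.72 and 5.0 × 14 / 52.18 = 1.34.

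These are illustrations. The hard limit is the planned 40 or so subjects in that age group.

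**How long until a form that criterion 13 names?** Visits 6, 7, 8 and 9 fall at Weeks 6, 10, 14 and 18, so 4 weeks apart. Visit 3 (Week 2) to Visit 6 (Week 6) is also 4 weeks when neither intermediate visit is held, since "Visits 4 and 5 are optional and will only be required if a subject requires further LCM dose adjustment" (Table 5-1, footnote c). The telephone contacts in between do not include the scale: for Weeks 8, 12 and 16, "The assessments for these telephone contacts are the same as those performed during the telephone contact at Week -3", and the Week -3 list in 8.1.2 has no C-SSRS. That list does include AE reporting and review of withdrawal criteria. When the next 'Since Last Visit' form is completed, it may not recapture the earlier answer, judging by its name.

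The documents give no basis for the number of attempts, or for how often one occurs without a Question 4 or 5 'Yes'.

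**The case against.** The strongest reply is that a wording asymmetry is not a child left on drug. Neither document reproduces the C-SSRS items, so how often a recorded attempt comes without a Question 4 or 5 'Yes' is unknown; often the two may coincide and criterion 13 would apply. This stands, and it limits what can be said about consequences.

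The other routes are also substantial. Criteria 1, 2 and 8 are must-withdraw rules once met: an intolerable AE, a sponsor or regulator request, or the investigator's decision on best interest. The first may-withdraw criterion covers psychiatric change. An attempt meeting a seriousness criterion, including important medical event, must reach the sponsor within 24 hours (Protocol 11.2.1 and 11.2.2) and enters ongoing SAE review (11.1.8). An Unscheduled Visit due to an AE makes the C-SSRS compulsory (8.5). The telephone contacts at Weeks 3, 8, 12 and 16 fall inside the 4-week intervals. All this narrows the gap, mainly to attempts judged non-serious, but each route to withdrawal still turns on someone's judgment and none mandates referral. Criterion 13 exists because ideation was not left to that.

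The shared wording may also be deliberate: the rationale for Amendment 2 (Protocol 17.3) aligned the suicidality text across the sponsor's protocols. That makes it a defensible choice and adds a cost to changing it. It does not explain why behavior was left out.

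A reader might infer that attempts during Baseline are unguarded, or that attempts would go unreported. The documents support neither. Exclusion 8 still applies at the Visit 2 check. Attempts reported as TEAEs are tabulated, and SAP Table 13-1 places suicidality terms among the other significant TEAEs (SAP 8.2.2).

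**Conclusion.** The point holds as a gap in a mandatory rule. After first dose, criterion 13 is the only suicidality-specific stop-and-refer rule, and it reaches neither an on-study attempt nor a Question 4 or 5 'Yes' on the 'Already Enrolled' form. This rests on the current text alone and is firm.

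Its practical size is small. Attempts are expected to be rare. The 'Already Enrolled' part is minor: one visit each for about 1 child, under an assumed even age spread. For that child, withdrawal could wait about 4 weeks for the next scheduled form that criterion 13 names, unless judgment or an Unscheduled Visit intervened.

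It would be tempting to conclude that the protocol keeps a child on LCM after an attempt. It does not: it leaves the decision to the investigator and sponsor, with several prompts to make it. The study's objectives and planned analyses are unaffected. This is a cheap, worthwhile improvement and not a serious defect.

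**What to change.** Reword the first sentence of criterion 13 along these lines: 'For subjects ≥6 years of age, a Yes to Question 4 or Question 5 on the Since Last Visit or Already Enrolled version of the C-SSRS, or any actual, interrupted or aborted suicide attempt occurring after enrollment.' Keep the referral and withdrawal sentence as it is.

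The attempt clause is tied to events after enrollment because the documents do not state how far back the 'Already Enrolled' form looks. Without that limit, a child could be withdrawn for an attempt that predates the study.

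The change uses data already collected and adds no visit or assessment. It alters a withdrawal criterion, so it needs an amendment approved by the sponsor, the IRB/IEC and, where required, regulators (Protocol 14.5); it can be bundled with the next one. It departs from wording shared across the sponsor's protocols. Its clinical cost is a rare extra withdrawal, with loss of discretion in that case for a child with uncontrolled epilepsy who may be benefiting from LCM.

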7 STUDY TREATMENT(S)

7.1 Description of IMP(s)

The oral solution formulation contains 10mg/mL of drug substance and is colorless to pale yellow in appearance. Oral solution doses will be measured and administered via a dosing syringe. The tablet formulation will be supplied in doses of 50mg and 100mg. The 50mg tablets are light pink, oval, film-coated tablets debossed with "SP" on one side and "50" on the other. The 100mg tablets are dark yellow, oval, film-coated tablets debossed with "SP" on one side and "100" on the other.

7.2 Treatment(s) to be administered

Lacosamide will be administered orally bid (at approximately 12-hour intervals in the morning and in the evening). Administration of oral solution by feeding tube is permitted for subjects who are unable to swallow the oral solution. At the end of the Baseline Period and completion of Visit 2, subjects who meet the eligibility criteria will commence a 6-week Titration Period (LCM dosing flexibility allowed based on tolerability).

As described in Section 5.1, subjects will initiate treatment with LCM oral solution at 2mg/kg/day, or LCM tablets at 100mg/day based on body weight. The dose will be titrated to a level to optimize tolerability and seizure control, not to exceed 12mg/kg/day (oral solution) for subjects weighing <50kg, or 600mg/day (tablets/oral solution) in subjects weighing ≥50kg. Subjects will increase the LCM dose in a stepwise fashion on a weekly basis to optimize tolerability and seizure control (see Figure 5-1 and Figure 5-2). During the Titration Period only, back-titration is permitted.

The planned doses for each week of the Titration Period for subjects taking the LCM oral solution and tablet formulations are displayed in Table 7-1.

Table 7-1: Lacosamide dose titration during the Titration Period

Body weight category (formulation)	Flexible doses for the Titration Period by study week					
	Week 1	Week 2	Week 3	Week 4	Week 5	Week 6
<50kg (oral solution)	2mg/kg/day	4mg/kg/day	6mg/kg/day	8mg/kg/day	10mg/kg/day	12mg/kg/day
≥50kg (tablets/oral solution)	100mg/day	200mg/day	300mg/day	400mg/day	500mg/day	600mg/day

LCM=lacosamide

Note: Subjects weighing ≥50kg who are unable or unwilling to swallow tablets can be dispensed LCM oral solution instead.

After completion of Week 1, investigators will assess whether a subject would tolerate a further dose increase or whether a subject should hold the Week 1 dose for a longer duration. This hold will be at the investigator's discretion. The flexible LCM dosing over the remainder of the Titration Period is outlined in Table 7-2.

Table 7–2: Flexible LCM dosing during the Titration Period

Body weight category (formulation)	Target dose increase/week ^a (titration)	Dose decrease per back-titration step		Subsequent dose increase ^b (dose increase after back -titration step)	
		Min	Max	Min	Max
<50kg (oral solution)	2mg/kg/day	1mg/kg/day	2mg/kg/day	1mg/kg/day	2mg/kg/day
≥50kg (tablets/oral solution)	100mg/day	50mg/day	100mg/day	50mg/day	100mg/day

LCM=lacosamide; Max=maximum; Min=minimum

^a Titration step to achieve a dose not previously administered^b Titration step subsequent to a back-titration

Note: Asymmetrical dosing with no more than 50mg difference between morning and evening doses will be allowed for subjects taking tablets who require back-titration in a 50mg increment (ie, only 50mg and 100mg tablets are available)

There is no limit to the number of back-titration steps or dose holds allowed and all are at the investigator's discretion; however, subjects must achieve the minimum LCM target dose for their body weight category by the end of the Titration Period. If it becomes apparent that a subject will not be able to reach the minimum target dose, then the subject should be withdrawn from the Titration Period and enter the Taper Period.

Subjects who have LCM titrated to a higher dose not previously administered should remain at that dose for ≥7 days unless a back-titration step is required based on tolerability. Subjects who have LCM back-titrated must remain on the lower dose for ≥3 days (in order to reach steady state) before a subsequent dose increase. After back-titration, subjects who return to a higher dose previously administered must maintain that dose for ≥3 days before subsequent titration to a higher dose.

As outlined in Table 7-3, subjects will be required to achieve and maintain at least a minimum LCM dose for at least the final 3 days of Week 6 to be eligible for entry into the Maintenance Period. Subjects may have a back-titration step as late as the last day of Week 6, as long as the minimum target dose is maintained.

Table 7–3: Required LCM dose for at least the final 3 days of Week 6

Body weight category (formulation)	LCM for at least the final 3 days of Week 6	
	Minimum	Maximum
<50kg (oral solution)	4mg/kg/day	12mg/kg/day
≥50kg (tablets/oral solution)	200mg/day	600mg/day

LCM=lacosamide

Eligible subjects (those who reach and maintain at least the minimum LCM dose for at least the final 3 days of the Titration Period) will enter a 12-week Maintenance Period at the dose they achieved at the last day of Week 6. The LCM dose will remain stable throughout the Maintenance Period. Subjects who require a change in dose during the Maintenance Period

will be withdrawn from the study. Subjects who require a change in formulation during the Maintenance Period should consult the medical monitor to assess if the subject can continue in the study. Subjects may be eligible for participation in the additional open-label study (SP848) if they have completed the Maintenance Period and are taking a minimum dose of 4mg/kg/day for subjects weighing <50kg, and 200mg/day (tablets/oral solution) for subjects weighing ≥50kg. Subjects will begin SP848 on the LCM dose they were taking in the Maintenance Period in SP0966. Subjects who do not complete the full 12 weeks of the Maintenance Period may still be eligible to enter the SP848 open-label study after consultation with the medical monitor.

Subjects who choose not to participate in the open-label study or subjects who discontinue due to other reasons will enter a 2- to 4-week Taper Period followed by a Safety Follow-Up Visit 2 weeks (±2 days) after the final dose of LCM and a Safety Follow-Up Telephone Contact 30 days (-1/+3 days) after the final dose of LCM. The doses to be used during the Taper Period and the duration of the Taper Period will depend on the dose maintained during the Maintenance Period.

Table 7-4 and Table 7-5 display the recommended LCM dose reductions during the Taper Period for subjects <50kg and ≥50kg, respectively. A slower taper is permitted if medically necessary. Whenever possible, these cases should be discussed with the medical monitor prior to withdrawing the subject from the study, especially in cases in which exit criteria have been met. In case of an emergency, a faster taper is permitted after discussion with the medical monitor, whenever possible. Taper of LCM may not be required for some subjects who discontinue study medication prematurely, depending on the treatment option selected by the investigator in consultation with the subject and/or parent/legal representative.

Table 7-4: Recommended LCM dose taper for subjects <50kg receiving oral solution formulation

Maximum LCM dose achieved	Taper schedule			
	Week 19	Week 20	Week 21	Week 22
11-12mg/kg/day	9mg/kg/day	6mg/kg/day	4mg/kg/day	2mg/kg/day
9-10mg/kg/day	8mg/kg/day	6mg/kg/day	4mg/kg/day	2mg/kg/day
7-8mg/kg/day	6mg/kg/day	4mg/kg/day	2mg/kg/day	2mg/kg/day
5-6mg/kg/day	4mg/kg/day	2mg/kg/day	2mg/kg/day	NA
3-4mg/kg/day	2mg/kg/day	2mg/kg/day	NA	NA

LCM=lacosamide; NA=not applicable (taper not required)

Note: Subjects with doses <3mg/kg/day do not need to taper. End of Taper Visit will be at the end of Week 22 for subjects undergoing 4 weeks of taper, at the end of Week 21 for subjects undergoing 3 weeks of taper, and at the end of Week 20 for subjects undergoing 2 weeks of taper.

Note: Subjects not requiring taper will enter directly into the Safety Follow-Up Period and not attend any Taper Period visits.

Note: The study week numbers provided are for subjects who complete the Maintenance Period and enter the Taper Period. The study week numbers provided do not apply to subjects who enter the Taper Period at other times.

Table 7–5: Recommended LCM dose taper for subjects ≥50kg receiving oral solution or tablet formulation

Maximum LCM dose maintained	Taper schedule			
	Week 19	Week 20	Week 21	Week 22
550-600mg/day	500mg/day	300mg/day	200mg/day	100mg/day
450-500mg/day	400mg/day	300mg/day	200mg/day	100mg/day
350-400mg/day	300mg/day	200mg/day	100mg/day	100mg/day
250-300mg/day	200mg/day	100mg/day	100mg/day	NA
150-200mg/day	100mg/day	100mg/day	NA	NA

LCM=lacosamide; NA=not applicable (taper not required)

Note: Subjects with doses <150mg/day do not need to taper. End of Taper Visit will be at the end of Week 22 for subjects undergoing 4 weeks of taper, at the end of Week 21 for subjects undergoing 3 weeks of taper, and at the end of Week 20 for subjects undergoing 2 weeks of taper.

Note: Subjects not requiring taper will enter directly into the Safety Follow-Up Period and not attend any Taper Period visits.

Note: The study week numbers provided are for subjects who complete the Maintenance Period and enter the Taper Period. The study week numbers provided do not apply to subjects who enter the Taper Period at other times.

